6.2.6 Additional review bodies

US National Institute of Mental Health (NIMH). The following events will be reported to the NIMH, this study's sponsor, as follows:

Event	Details	Reported By
IRB Suspension or Termination	If ethics approval is suspended or termination, a statement of reason(s) for the action must be reported to the NIMH Program Officer (PO) within 3 business days of suspension/ termination receipt .	PIs and SAMRC ethics board
Deaths related to study participation	Within 48 hours of PIs becoming aware of death.	PIs
Unexpected SAEs related to study participation	Reported to the NIMH PO within 10 business days of the study team becoming aware of the SAE.	PIs
Unanticipated Problems involving risks to subjects or others	Reported to the NIMH PO within 10 business days of the PI becoming aware of event.	PIs
Serious or Continuing Noncompliance	Reported to the NIMH PO within 10 business days of ethics determination .	SAMRC ethics board
AEs and SAEs	A summary of all AEs and SAEs that are deemed expected and/or unrelated to the study should be submitted to the NIMH PO and the SAMRC ethics board with the annual progress report .	PIs
Protocol Violations	Annual progress report.	PIs

6.3 Responsibility

The Multi-PIs (MPIs) are ultimately responsible for data and safety monitoring. The processes described above ensure that the MPIs will be aware of important study related issues on a regular basis.

6.4 Disclosure of any conflict of interest

Each investigator will complete a conflict of interest statement which will be kept on file by the study team. Any new investigators or key study staff will complete these forms, which will be stored and kept on record. At this time, there are no conflicts of interests in this study.

7. Timeline

Initial Training:

Week	Task	Amount of Time
Week 1		
Week 2	Finalize training manual, set training date, and recruit CHWs	1 month
Week 3		
Week 4		
Week 5	Training (including pre-training and post-training assessment)	3 – 5 days
Week 6		
Week 7	Weekly supervision, roleplays, audio-recordings, and patient	
Week 8	consents/ assessments	1-month
Week 9		
Week 10	1-Month Follow-Up Assessment	~30min per CHW

Upon receiving ethics approval for stepped-wedge trial, approximate timeline:

Month	Group 1 ~20 CHWs	Group 2 ~20 CHWs	Group 3 ~20 CHWs
1			
2		Finalize minor adaptions to training manual, work with NGOs and Western Cape Department of Health, recruit CHWs	
3	Baseline Assessment + TAU	Baseline Assessment + TAU	Baseline Assessment + TAU
4	TAU	TAU	TAU
5	Pre-Treatment Assessment + Training + Supervision	TAU	TAU
6	Supervision	Pre-Treatment Assessment + Training + Supervision	TAU
7	Supervision	Supervision	Pre-Treatment Assessment + Training + Supervision
9	3MFU	Supervision	Supervision
10		3MFU	Supervision
11			3MFU
12	6MFU		
13	Stakeholder (CHW and providers) interviews	6MFU	
14		Stakeholder (CHW and providers) interviews	6MFU
15			Stakeholder (CHW and providers) interviews

TAU = treatment as usual

8. Management Details

8.1 Management Approach

The present study will be led by the two PIs: [name] and [name].

8.1.1 SAMRC

[name] (MPI) will take primary responsibility for SAMRC ethics protocols, training materials, staff training and management, and quality assurance. They will also oversee data collection.

8.1.2 UMD

[name] will oversee data management and the US based team who will support administrative coordination, oversight on regulatory issues and compliance, and all data management and cleaning.

8.3.1 Both Sites

Dissemination & Implementation. Drs [name] and [name] will work collaboratively on the dissemination of findings. Specifically, each PI will take responsibility for gathering and coordinating resources and ensuring outputs for each area of primary responsibility. Leadership will be shared, as will responsibilities, authority, data, and credit. All final scientific and study implementation decisions will be made collaboratively between PIs, with inputs from the project team.

Communication. The PIs will communicate on a regular basis regarding study implementation and progress by telephone or video, in addition to regular email communication. Depending on travel guidelines (due to COVID-19 or other events), team members who are not located in South Africa will travel to Cape Town to support study training and implementation.

Conflict Resolution. All final decisions will be made collaboratively between Drs [name] and [name]. In the case of conflicts, the two PIs will work diligently to resolve any issues and will draw on the expertise and inputs of the Co-Is and study collaborators to reach consensus. In the unlikely case that the two PIs cannot come to a consensus, they will seek out a third-party mediator ([name] at the University of Cape Town) to help resolve this conflict.

8.2 Staff and Scientific Collaboration

[name] (MPI) will have the overall responsibility of ensuring procedural and scientific integrity of the SA-based study operations, including overseeing the team at the SAMRC. This will include supporting training and supervising research staff on study measures and assisting with regulatory requirements.

[name] (United States PI) will have the overall responsibility of ensuring the procedural and scientific integrity of the US-based study operations, including data management and oversight. She will lead the team at UMD in coordinating research meetings, maintaining a study timeline, creating reports on study projects, handling ethics committee issues, and ensuring clear communication between all study members.

8.3 Facilities

8.3.1 Field Site

The present study team will be based on the SAMRC premises in Delft. This site has all the privileges of SAMRC office space and is the base for several studies located within the community. Project staff will be housed at this facility.

Please note that due to COVID-19, staff may work remotely. If working remotely, staff will still have access to SAMRC resources.

8.3.2 Data Management Site

Data management will primarily occur in the Global Mental Health and Addiction Program (Director: [name]) at UMD. The office space consists of shared office space, a conference room, individual offices, and locked file storage rooms. Data files will be saved to a secure network running the PI's laboratory.

Please note that due to COVID-19, staff may work remotely. If working remotely, staff will still have access to UMD resources including access to the secure network.

9. Additional Details

9.1 Research Translation

9.1.1 Manuscripts.

We plan to publish the findings of this study in peer-reviewed journals. At a minimum we hope to publish a mixed-methods report of the implementation (i.e., acceptability and feasibility) findings of this pilot study. At a minimum we will publish a report of the implementation and preliminary effectiveness findings of the study.

9.1.2 Scientific Conferences.

We plan to present findings from this study at scientific conferences, including Addiction Health Services Research (AHSR) annual meeting, the Dissemination & Implementation Science Annual Conference, and the College of Problems on Drug Dependence (CPDD).

9.1.3 Training Materials.

This study will allow for the final adaptation of our training program for CHWs. We will use this final adaption in the next phase of the study with more CHWs (for which we will receive separate ethics approval). If at the end of this future study the approach proves to be effective, feasible, and acceptable, we will offer capacity-building workshops to train CHWs in the adapted manual, using a version that incorporates stakeholder feedback of feasibility and acceptability.

9.1.4. Data Sharing Plan.

We will make de-identified transcripts, codebooks, and quantitative data available to interested individuals (with appropriate training and approvals) after publication of the main outcome paper(s). Data will be released directly by the investigators providing evidence of their institution's ethics approval for planned analyses of the data. Our team will be available to address queries.

9.1.5. Clinical Trial Registration

In line with the requirements of the US National Institutes of Health (NIH), Part II of this study (Stepped Wedge Design) will be registered on ClinicalTrials.gov within 21 days of enrolment of the first participant.

Appendix 1: Budget Documents

Please see attached budget documents.

Appendix 2: Procedures for Distressed Participants

Procedures for Distressed Participants and Mandatory Reporting

Given the nature of this study, there may be instances, where you as a researcher are faced with a distressed participant who you are concerned needs additional or immediate mental health support. For the most part, you can address this by talking to the participant and providing them with a referral to see the mental health nurse or for additional substance abuse services.

1. What is a distressed participant?

By “distressed” we mean that a participant shows signs of experiencing negative emotions and by his/her words, expressions, or other nonverbal behaviors or body language indicates that s/he is emotionally upset.

Possible signs or indications of distress:

- A participant who is tearful and/or reports that s/he feels badly or is sad
- A participant who shows signs of being considerably more nervous or anxious (e.g., very nervous speech, increased sweating, difficulty sitting still during the appointment) than would be expected during an appointment.
- A participant who seems agitated or aggressive and that you cannot easily calm down.

1.1 Steps to follow with mildly distressed participants who need additional services

In most cases of distress, participants may talk about feeling badly but you will be able to manage or contain these feelings and continue with the appointment. They may however, need additional services or support once the counselling intervention has been completed.

In these cases, complete the following steps at the end of the study appointment:

- Indicate to the person that they seem upset or anxious
- Discuss with the participant the importance of additional support
- Ask if they would like to receive additional services to talk more about feelings that came up during the course of the study
- If the participant indicates s/he would like to talk with someone further, ask if they would like you to refer them to an organization
- Complete the referral and release form
- With the participant’s permission, call the agency or the clinic nurse to make an appointment
- Provide the patient with a copy of the referral letter in an envelope and keep one in the participant’s file
- Provide the participant with a copy of the resource guide for additional services
- If the participant indicates that s/he does not want you to make a direct referral, suggest various organizations for him/her to contact on her own and give them a copy of the resource guide.
- At the end of the appointment, document this referral in the Participant’s file

These steps should only be followed if the participant shows signs of distress or expresses a need for more counselling- but ***no suicidal intent or imminent harm is disclosed or suspected.***

If the person expresses any desire to end their life or hurt themselves or others, follow the steps described in 1.2 and the mandatory reporting procedures described in section 2.

1.2 Steps to follow with very distressed participants

There may be instances where participants are so distressed that you are concerned for their safety and may not be able to continue with the appointment. Remember that we have made it clear in the consent form that there are exceptions to our promise of confidentiality. If participants express the intent to harm themselves or others, or ongoing abuse and/or neglect of children, then we have a duty to report this matter to the proper authorities, e.g. the police, courts or social workers. Field staff will provide information on toll-free hotlines that people can call to talk to someone and seek assistance, as well as local resource information.

If during the course of the study you are concerned that a participant intends to harm him/herself or others, then mandatory reporting procedures need to be followed on completion of the appointment. Immediately inform the project manager and the principal investigator (PI) who will report the incident to the various ethics committees and our project officer within 72 hours.

In these instances, please follow the following steps:

- As far as possible, complete the study appointment
- Indicate to the person that they seem upset or anxious
- Remind the person of the limits of confidentiality as expressed in the consent form, and your duty to report
- Follow the mandatory reporting procedures described below
- Complete the referral and release form
- Call the agency to make an immediate appointment
- Provide the patients with a copy of the referral letter in an envelope and keep one in the participants folder
- Provide the patient with a copy of the resource guide for additional services
- At the end of the appointment, document this referral in the Participant's file
- Complete an incident report form and immediately send to the project manager and PI who will both keep copies on file and will report the incident to the relevant regulatory bodies.

2. Mandatory reporting procedures

It is possible that a participant will indicate during the course of a discussion that s/he is in immediate danger of harm or poses a threat to the safety of others. We want you to feel that you can handle this situation with confidence.

There are essentially three situations in which there may be immediate danger of harm:

- 1) **Suicidal Intent:** The participant expresses a desire to hurt or kill themselves.
- 2) **Hurtful Intent to Others:** The participant expresses an interest in hurting or killing someone else (not necessarily someone living in the household).
- 3) **Child Abuse and Neglect:** Ongoing abuse and/or neglect of children.

The rest of this protocol describes what to do in each of these cases. For each of these cases, you must follow compulsory or mandatory reporting procedures.

These procedures are important to follow because they take away the responsibility of you having to decide what to do. These procedures are in your best interest and in the best interest of the participant- they are to keep the participant safe and unharmed.

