2.2.2 IMMEDIATE RISK

If immediate danger is perceived please alert the project manager and the PI immediately and they will report the incident to the authorities. Do not let the participant leave before you have instructions from the police or the trial manager as to next steps to take. Please follow each of these steps.

Script: Risk of someone being harmed or killed revealed by participant during the appointment

Project manager or PI to read to the authorities

"We are conducting a research study, and during an appointment, a participant expressed that s/he intended to harm or kill someone, so we are alerting you.

Please note that this information was obtained during an appointment that was conducted for this research study. We went through appropriate informed consent procedures, including telling the participant that a report might be made if the information s/he provided indicated that s/he might harm themselves or others. I can give you additional information about the research study, if you would like. The participant is here at the moment."

It is unlikely that you will be faced with this situation!

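### Appendix 2 gives conflicting timing for acting on an intent to harm self or others, and no sentence says which timing has priority

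*Combined protocol and SAP*

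**What the plan says.** All of the relevant text is in Appendix 2 (Procedures for Distressed Participants).

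- **Section 1.1** covers mild distress. For any expressed wish to die, or to hurt oneself or another person, it tells staff to "follow the steps described in 1.2 and the mandatory reporting procedures described in section 2". Both sets of instructions therefore apply to the same disclosure.
- **Section 1.2** covers severe distress. It opens by recognising cases where "participants are so distressed that you are concerned for their safety and may not be able to continue with the appointment". On concern about intent to harm, "then mandatory reporting procedures need to be followed on completion of the appointment". The next sentence reads "Immediately inform the project manager and the principal investigator (PI) who will report the incident to the various ethics committees", with a 72-hour limit for that onward report. The step list then begins "As far as possible, complete the study appointment"; the mandatory reporting procedures are its fourth item.
- **Sections 2.1 and 2.1.1** cover suicidal intent. They set out risk questions and then a hotline script. If a participant at immediate risk will not use the hotline, staff must contact the project manager immediately. Neither section mentions completing the appointment.
- **Section 2.2** covers intent to harm others. Its list has the same first step as 1.2. Exploring whether the risk is immediate is the third item.
- **Section 2.2.1** (no immediate danger) still requires the project manager and PI to be advised immediately.
- **Section 2.2.2** (immediate danger) says "If immediate danger is perceived please alert the project manager and the PI immediately and they will report the incident to the authorities".

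**The concern.** These are working instructions for field staff at the moment of a disclosure. The introduction to section 2 tells staff that the procedures relieve them of having to choose a course of action, so the text has to give one order of events. If some sentences place the risk check and the notification after the appointment and others place them at once, two staff members can each comply and still act in different orders. On one of those orders, completing a research visit comes before the step that would show whether the matter is urgent. What is at stake is participant and third-party safety, not the trial's inference.

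**Working it through.** No formula or planned figure is involved in the contradiction itself. The check sets the instructions side by side, by type of disclosure, and asks whether any sentence settles the order.

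**1. Section 1.2 on its own.** One sentence places mandatory reporting at the end of the appointment. The next calls for immediate notification of the project manager and PI. These might be two separate actions: tell the team now, report formally later. But the mandatory reporting procedures are the contents of section 2, and for harm to others (2.2.1 and 2.2.2) those contents include immediate notification of the same two people. The same action is then timed both ways.

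**2. Intent to harm others.**

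| Source | Action | Timing in the text |
|---|---|---|
| 1.2, body text | Mandatory reporting | After the appointment, unqualified |
| 1.2 and 2.2, first list item | Complete the appointment | First, so far as it can be done |
| 2.2, third list item | Check for immediate risk | Listed after completion |
| 2.2.1 | Tell project manager and PI | Immediately, even with no immediate danger |
| 2.2.2 | Alert project manager and PI | Immediately, on perceiving danger |

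Staff reach 2.2.1 or 2.2.2 only by making the risk check. Taken in listed order, that check follows completion of the visit. The instruction to act at once thus depends on a step placed after the one it might need to override.

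**3. Intent to harm self.** Section 2.1 contains no completion step, so the conflict does not arise within it. It arises because 1.1 sends these disclosures to 1.2 as well. Staff then hold 1.2's completion rule together with 2.1's risk questions, and with 2.1.1's immediate contact for a participant who is unwilling to use the hotline. Neither section says whether the questions interrupt the appointment.

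**4. Is there a priority rule?** I found none in sections 1.1 to 2.2.2. Nothing says that section 2 overrides 1.2, or the reverse.

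**5. Size of the possible delay.** If a visit lasts L minutes and the disclosure comes after a fraction f of it, completing the visit takes a further L × (1 − f) minutes. The documents give two values of L, both for the initial pilot: about 40 minutes (section 3.5.1c, pre-assessment) and about 30 minutes (section 7, 1-month follow-up). The values of f are assumptions.

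| f | L = 40 | L = 30 |
|---|---|---|
| 0 (start of visit) | 40 × 1 = 40 min | 30 × 1 = 30 min |
| 0.5 (midway) | 40 × 0.5 = 20 min | 30 × 0.5 = 15 min |
| 1 (end of visit) | 0 min | 0 min |

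For the stepped-wedge trial, section 3.5.2b gives about 10 minutes for the roleplay but no length for a whole visit, so the delay there cannot be stated.

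**The case against.** The strongest reply is that the text, read sensibly, is workable.

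- **The completion step is qualified.** Both lists say "As far as possible, complete the study appointment", and 1.2 accepts that staff "may not be able to continue with the appointment". This stands: finishing the visit is not absolute. But the body sentence in 1.2 carries no qualifier, and a calm participant who discloses a plan may be quite able to finish.
- **A sequential reading exists.** In 1.2, immediate notification may mean immediately once the appointment ends. This is possible, but the text does not say it, and 2.2.1 and 2.2.2 tie immediacy to the assessment of danger rather than to the end of the visit.
- **The specific rule governs the general.** Section 2.2.2 is more specific than 1.2 and could be taken to prevail. That is a reasonable convention, but it is not stated, and the risk check leading to 2.2.2 is itself listed after completion.
- **Other safeguards exist.** The protocol's section on psychological discomfort (5.2.3) provides for monitoring of distress, staff training, registered counsellors and daily clinical oversight. Appendix 2 also says that at-risk participants must not be left alone or allowed to leave. These lower the risk. However, the training is in this same procedure, and oversight begins to help only when the team is contacted, which is the timing in doubt.

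Three stronger readings are not supported:

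- A reader might infer that severe distress simply waits for the end of the visit, as mild distress does. It does not: the severe path's completion step is qualified, and mandatory reporting and immediate notification are added.
- A reader might infer that section 2.3 on child abuse has the same fault. It places reporting after the appointment throughout, so it is consistent on timing.
- A reader might infer that section 2.1 requires the project manager to be contacted at once for every self-harm disclosure. That instruction applies to a participant who is unwilling to use the hotline.

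**Conclusion.** The point holds as an unresolved contradiction on timing. It is most direct for intent to harm others, where 1.2 and 2.2 put the appointment first and 2.2.1 and 2.2.2 require immediate notification. For self-harm it arises through 1.1, which applies 1.2 alongside section 2. That staff would actually continue collecting data after a disclosure is an inference from the order of the listed steps; the documents do not say that it will happen.

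The possible delay is bounded by what remains of a visit: at most about 40 or 30 minutes for the two initial-pilot assessments with a stated length, and unknown for the stepped-wedge trial. Such disclosures may be rare; the documents give no expected frequency. Sample size, power and error rates are untouched. The case for acting rests on the seriousness of the event and the small cost of the repair. This review takes no position on which timing is clinically right.

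**What to change.** Reconcile Appendix 2 sections 1.1, 1.2, 2.1 with 2.1.1, and 2.2 with 2.2.1 and 2.2.2, so that each type of disclosure has one order of actions. For each type, state where the risk check falls relative to the appointment, and where notification of the project manager and PI falls relative to it. State also whether section 1.2 or section 2 governs if they differ. The content should be decided by the team's responsible clinician.

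The cost is a rewording of the appendix, an amendment submitted to the ethics committee before use (as section 6.2.2 requires for any change) and a short re-brief of staff. No change to the design, data collection or analysis is needed.
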